13.3 Secondary and Tertiary Efficacy Endpoints

13.3.1 Annualized Bleeding Rate and FVIII Utilization

The first three secondary efficacy endpoints are:

- The change from baseline (prior to BMN 270 infusion while receiving FVIII prophylaxis) in the annualized utilization (IU/kg/year) of exogenous FVIII replacement therapy in the efficacy evaluation period (“Post-FVIII prophylaxis period”)
- The change from baseline (prior to BMN 270 infusion while receiving FVIII prophylaxis) in the annualized number of bleeding episodes irrespective of exogenous FVIII replacement treatment (annualized bleeding rate, ABR for all bleeds) in the efficacy evaluation period (“Post-FVIII prophylaxis period”)
- The change from baseline (prior to BMN 270 infusion while receiving FVIII prophylaxis) in the annualized number of bleeding episodes requiring exogenous FVIII replacement treatment (annualized bleeding rate, ABR) in the efficacy evaluation period (“Post-FVIII prophylaxis period”)

The annualized utilization (IU/kg/year) of exogenous FVIII replacement therapy is defined as

$$\frac{\text{Sum of FVIII use (IU/kg) during calculation period}}{\text{Total number of days during the calculation period}} \times 365.25$$

The annualized number of bleeding episodes (for all bleeds and treated bleeds), i.e., annualized bleeding rate (ABR for all bleeds and treated bleeds), is defined as

$$\frac{\text{Number of bleeding episodes (all bleeds or treated bleeds) during the calculation period}}{\text{Total number of days during the calculation period}} \times 365.25$$

The calculation period in the above formulas for the post-baseline value is:

- For the primary analyses, the efficacy evaluation period “Post-FVIII prophylaxis period” as defined in Section 13.1.
- For the supportive analyses, other efficacy evaluation periods as defined in Section 13.1.

If a post-baseline value is missing, e.g., when a subject drops out before Week 5, the change in ABR and annualized FVIII utilization will be imputed as the median value of the changes of all subjects’ observed cases.

The baseline values of ABR and FVIII utilization for each subject will be derived based on the 12-month historical data prior to 270-303 study screening up until the BMN 270 infusion date.

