For the number of bleeding episodes, only treated bleeds will be considered. Bleeds due to surgery/procedure are not included. Only treatments that were recorded as “treatment for bleed” are included in the determination of a treated bleed. The definition of a “treated bleed” is as follows:

- If a bleed is directly followed by a hemophilia medication reported to be a “treatment for bleed” within 72 hours (or 3 calendar days if time is not available), it is considered to be a treated bleed. This bleed and the first treatment thereafter are referred to as a pair
- If multiple bleeds of different type or/and different anatomical location occur within 24 hours (of the last bleed before treatment for bleed) or on the same calendar day, the subsequent treatment within 72 hours (or 3 calendar days if time is not available) is considered to pair with each of these bleeds. Each of these bleeds that is within 72 hours (or 3 calendar days if time is not available) of the subsequent treatment is therefore considered to be a treated bleed

- Two bleeds of the same type and at the same anatomical location are considered to be one bleed if the second occurs within 72 hours (or 3 calendar days if time is not available) from the last treatment for the first bleed. The last treatment is defined as the last treatment before a new bleed occurs, either in the same or in a different location. This is regardless whether the second bleed is followed by a treatment

The changes from baseline in ABR and annualized FVIII utilization will be tested using Wilcoxon signed-rank tests (primary method) and one-sample t-tests (supportive method). Only negative changes indicate efficacy.

Supportive and sensitivity analyses on ABR (for all bleeds and treated bleeds) and annualized FVIII utilization will include:

The number of bleeding episodes and total FVIII utilization will be listed by subject and by periods (pre-BMN 270 infusion [baseline period], Weeks 1-4, Week 1 to end of original FVIII prophylaxis, and the efficacy evaluation periods as defined in [Table 13.1.1](#)). The ABR and annualized FVIII utilization (IU/kg/year) will be summarized descriptively by periods.

The changes from baseline in ABR (for all bleeds and treated bleeds) and annualized utilization (IU/kg/year) of exogenous FVIII replacement therapy will also be analyzed using data in different efficacy evaluation periods as defined in [Table 13.1.1](#).

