The ABR may be analyzed using a generalized linear mixed model assuming negative binomial as the underlying distribution. The model will include period (pre-BMN 270 infusion [baseline period], Week 1-end of FVIII Prophylaxis, Post FVIII Prophylaxis-Last Visit) as the only factor. The analysis will be performed using the SAS GENMOD procedure where the duration of each period is included as an OFFSET to account for varying follow-up times and a REPEATED statement is included to account for the intra-patient comparison.

The primary analyses on ABR and FVIII utilization may be conducted for the PP population when applicable.

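### The optional negative binomial bleed analysis contradicts itself on model type, and its stated response and offset do not add up to a rate model

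*SAP*

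**What the plan says.** All references are to SAP version 2.0; version 1.0 has the same wording for this model.

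- Model and response (Section 13.3.1): "The ABR may be analyzed using a generalized linear mixed model assuming negative binomial as the underlying distribution".
- Factor: "The model will include period (pre-BMN 270 infusion [baseline period], Week 1-end of FVIII Prophylaxis, Post FVIII Prophylaxis-Last Visit) as the only factor".
- Procedure: SAS GENMOD is named as the software procedure for the fit.
- Offset and clustering: "the duration of each period is included as an OFFSET to account for varying follow-up times and a REPEATED statement is included"; the stated purpose of REPEATED is to handle comparisons within the same patient.
- The ABR formula in the same section divides the number of bleeds by "Total number of days during the calculation period" and multiplies by 365.25.
- The formal comparison is elsewhere: the changes in ABR "will be tested using Wilcoxon signed-rank tests (primary method) and one-sample t-tests (supportive method").

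The section states no link function, unit for the duration, working correlation, standard error type or reference distribution for this model.

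**The concern.** Three parts of the description do not fit together.

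1. **Model type.** A generalized linear mixed model has subject random effects and a likelihood. GENMOD with a REPEATED statement solves generalized estimating equations and has neither. A programmer has to depart from either the label or the procedure.
2. **Response and offset.** Under a log link, a rate model takes the count as response and log(duration) as offset. The text names a response already divided by time and then adjusts for time again. It also enters the duration, not its log. A negative binomial response should be an integer count, which ABR generally is not.
3. **Standard errors.** At most 22 subjects contribute (Section 4.5 gives 22 actual, and the mITT may be smaller). GENMOD with REPEATED reports empirical (sandwich) errors by default, and these tend to be too small with so few clusters.

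This is the only planned bleed analysis that models over-dispersed counts. At stake are the rate ratio and confidence interval it would report.

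**Working it through.** **The plan's own figures.** The SAP gives no power or precision figure for this model. Its only power figure concerns FVIII activity: n = 16, effect size 0.8, two-sided 5%. With df = 15 and noncentrality 0.8 × √16 = 3.2, power is 84.8%, which agrees with the stated 85%. The present point does not touch it.

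**Period lengths.** Baseline runs from 12 months before screening to infusion (Section 5.5). The early period runs from Day 1 to at least Day 32 (Appendix 20.1). The post-prophylaxis period runs to the last visit by data cutoff (Table 13.1.1). Exact lengths are not in the SAP, so the day counts below are assumptions, except that 32 days is the planned minimum for the early period.

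**Step 1: effect of each literal reading.** Assume a log link and a true rate ratio of 1. Let T0 be the baseline length and T1 the comparison length. The fitted ratio is then:

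- count response, raw offset in years: (T1/T0) / exp((T1 − T0)/365.25)
- ABR response, log(duration) offset: T0/T1
- ABR response, raw offset in years: exp((T0 − T1)/365.25)

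| T1 vs T0 (days) | Count, raw years | ABR, log offset | ABR, raw years |
|---|---|---|---|
| Post 336 vs 400 | 0.84/0.839 = 1.00 | 1.19 | 1.19 |
| Post 700 vs 456 | 1.535/1.950 = 0.79 | 0.65 | 0.51 |
| Early 32 vs 400 | 0.08/0.365 = 0.22 | 12.5 | 2.74 |
| Early 60 vs 400 | 0.15/0.394 = 0.38 | 6.67 | 2.54 |

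With a raw offset in days, 400 and 336 days differ by 64 on the log scale. That is a factor of exp(64), about 10^28, where 400/336 = 1.19 is correct.

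With count response and log(duration) offset, the ratio is 1 in every row.

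**Step 2: simulation of the ratio.** Assumptions:

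- no true change, with 1, 3 or 5 bleeds per year
- between-subject gamma variance 1, and period-level gamma variance 0.5 or 1.5 (1.0 in the 16-subject run)
- periods of 1.10-1.35, 0.09-0.19 and 0.95-1.75 years
- 22 subjects, and one run with 16

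Median fitted ratios for a count response:

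- raw years: 0.87-1.02 for post versus baseline, and 0.31-0.37 for early versus baseline (at most 150 replicates per setting, so approximate)
- log(duration), 22 subjects: 0.97-1.02 and 0.97-1.03

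**Step 3: simulation of the test.** The fit is a negative binomial GEE with the correct log offset, exchangeable working correlation and working dispersion 1. The test is two-sided 5%, post versus baseline. There were about 730 to 1,060 usable replicates per setting (Monte Carlo standard error about 1 percentage point).

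| Subjects | Ordinary sandwich, normal reference | Bias-reduced sandwich, t(N−1) |
|---|---|---|
| 22 | 10.8-14.1% | 7.4-10.3% |
| 16 | 13.1% | 8.7% |

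Further runs under other assumed rates and dispersions widen these ranges to roughly 7-15% and 4-12%. A random-intercept model was not simulated.

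**The case against.** The strongest reply is that nothing formal depends on this model. It is worded as a possibility, sits among the supportive analyses, and carries no alpha or hypothesis. The ABR comparison rests on the Wilcoxon test.

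The text also says why duration is entered: to allow for varying follow-up. With a negative binomial distribution and an offset, a statistician would naturally read a count model with log exposure. A raw offset in days would fail visibly rather than give a plausible wrong answer. The silence on standard errors is a lack of detail, not a stated choice. All of this stands and limits the weight of the point. The mixed-model label still contradicts the named procedure, and the written response and offset still need correcting.

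A reader might infer more than the documents support:

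- **That the reported rate ratio will be wrong.** The SAP does not show how the model was programmed, and the link is not stated.
- **That the efficacy contrast is badly distorted.** The severe distortion belongs to the early period, which includes continued FVIII prophylaxis. For post-prophylaxis versus baseline at 1.1 and 1.25 years, the correct exposure ratio is 1.25/1.1 = 1.14 and a raw-year offset with a count response implies exp(0.15) = 1.16, a difference of about 2%.
- **That the plan prescribes uncorrected standard errors.** This is inferred from the procedure's default.
- **That follow-up is otherwise ignored.** ABR divides by days, so the Wilcoxon test and t-test already adjust each subject's value for follow-up length.

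**Conclusion.** Minor, but real. The description is internally inconsistent: a mixed model is named and a marginal GEE procedure is ordered. With a log link and a random intercept alone, the period rate ratio means the same in both, so the mismatch bears mainly on likelihood and standard errors.

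The response and offset, taken literally, do not estimate a rate ratio. The error is severe for the short early period and unusable in days. In years it is modest for post-prophylaxis versus baseline when the two lengths are similar, and it grows as they diverge. These sizes assume a log link and illustrative period lengths.

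The 7-15% false-positive range is conditional on default empirical errors, at most 22 subjects, and bleed rates and dispersions that the SAP does not give. The Wilcoxon test, the t-test and the primary FVIII analysis are not affected.

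**What to change.** Rewrite the paragraph in Section 13.3.1 so that the response is the number of bleeds in each period, the link is log, and the offset is log(duration) with its unit stated. Then choose one of two routes:

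- **GEE.** Call it that, state the working correlation, and use small-sample bias-corrected standard errors with a t reference. This reduces the inflation but did not fully restore 5% in most of the settings simulated.
- **Mixed model.** Fit a negative binomial model with a subject random intercept, in a procedure that supports random effects. Its small-sample behaviour was not checked here.

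The cost is one paragraph of SAP text, possibly a change of procedure, and somewhat wider confidence intervals. No data collection or primary analysis changes.

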13.3.2 Haemo-QoL-A and Other Patient-Reported Outcomes

The following patient-reported outcomes (PROs) will be used to assess subjects' quality of life (QoL) during the study:

- Change from baseline in the total score of HAEMO-QoL-A at Week 52 of the study post-BMN 270 infusion
- Change from baseline in the EQ-5D-5L score at Week 52 of the study post-BMN 270 infusion

- Change from baseline in the Work Productivity and Activity Impairment plus Classroom Impairment Questions: Hemophilia Specific (WPAI+CIQ:HS) score at Week 52 of the study post-BMN 270 infusion
- Change from baseline in Patient Reported Outcomes, Burdens, and Experiences (PROBE) score at Week 52 of the study post-BMN 270 infusion

The PROs will be assessed at baseline, Week 4, Week 12, Week 26, Week 52 and every 6 months starting with Week 76 per protocol-scheduled assessments.

The QoL endpoints including the sub-scale/sub-domain scores (except for PROBE) will be summarized descriptively for the mITT population using the observed cases by visit up to the data cutoff. The p-value and 95% CI for the change from baseline based on two-sided t-test will be provided for descriptive purposes. PROBE will be analyzed externally through a separate statistical analysis plan.

13.4 Other Efficacy Endpoints

13.4.1 FVIII Infusions

Total and annualized number of FVIII infusions will be listed by subject and by periods (pre-BMN 270 infusion [baseline period], Weeks 1-4, Week 1 to end of original FVIII prophylaxis, and the efficacy evaluation periods as defined in [Table 13.1.1](#)), and the annualized FVIII infusion rates will be summarized descriptively by periods.

The same analysis of FVIII utilization (IU/kg) and number of FVIII infusions will be performed for the following types of FVIII infusion in the primary efficacy evaluation period:

- Treatment for bleed
- Surgery/procedure
- Usual prophylaxis (routine)
- One-time prophylaxis

Analysis based on the type of FVIII product used will be performed if applicable.

13.4.2 Bleeds

The following types of bleeds will be analyzed:

- Treated joint bleeding episodes
- Treated target joint bleeding episodes (bleeding episodes that occur at joints which are listed as target joints at study entry)
- Treated spontaneous bleeding episodes

- Treated traumatic bleeding episodes

The analyses include tabulation of total and annualized counts by subject and by periods (pre-BMN 270 infusion [baseline period], Weeks 1-4, Week 1 to end of original FVIII prophylaxis, and the efficacy evaluation periods as defined in [Table 13.1.1](#)), and descriptive summary of the corresponding annualized rates. Target joint resolution with the incidence and percentage of the resolved target joints post BMN-270 treatment will be assessed.

13.5 Examination of Efficacy by Subgroups

Subgroup analyses will be performed on the efficacy endpoints including FVIII activity by chromogenic assay, annualized FVIII utilization (IU/kg/year) and ABR (for all bleeds and treated bleeds) based on the following baseline characteristics:

- Age at enrollment: ≥ 18 - < 30 years vs. ≥ 30 - < 50 years vs. ≥ 50 years old
- Target joint at baseline: Yes vs. No

Subgroup analyses based on other baseline characteristics may also be performed for exploratory purposes if the sample size permits.

14 SAFETY EVALUATIONS

Safety will be assessed by adverse event reporting; clinical laboratory assessments, with particular attention to the liver tests; vital signs assessments; and physical examinations. Safety analyses will be carried out for the ITT analysis population. No formal statistical testing will be performed; only summary statistics will be provided.

14.1 Adverse Events

Only treatment-emergent adverse events (TEAEs) occurring and reported during the study period will be included in the adverse event summaries. A TEAE is defined as any AE that newly appeared or worsened in severity following initiation of study drug administration. Adverse events will be coded in accordance with MedDRA.

An adverse drug reaction (ADR) is any AE for which there is a reasonable possibility that the study drug caused the AE. The investigator will assess the causality for individual AEs, applying the guidance specified in protocol, and those assessed as IP-related will be considered ADRs.

A serious adverse event (SAE) is any untoward medical occurrence that at any dose meets one or more of the seriousness criteria enumerated in the protocol. AE severity, not equivalent to seriousness, will be assessed using the protocol defined categories using the NCI CTCAE v4.03.

All bleeding events and suspected bleeding events, regardless of the need for exogenous FVIII therapy as treatment, should be captured in subject diaries and recorded on the designated bleeding electronic case report form (eCRF). Bleeding events and suspected bleeding events should not be reported as adverse events, with the following exception:

- All bleeding events and suspected bleeding events which meet one or more of the criteria for being serious (refer to the protocol Section 10.2) should be reported as serious adverse events (whether or not they are bleeding events that are normal sequelae of hemophilia, and whether or not they require exogenous FVIII as treatment).

The study AE reporting period is as follows: After informed consent but prior to initiation of study treatment, only SAEs associated with any protocol-imposed interventions will be reported. After informed consent is obtained and following the administration of study drug, the reporting period for all non-serious AEs and SAEs begins and continues for approximately 5 years or until study discontinuation/termination.

The following types of AEs will be summarized: all AEs, AEs assessed by investigator as related to BMN 270, SAEs, SAEs assessed by investigator as related to BMN 270, AEs leading to study discontinuation, deaths, and events of special interest (EOSI), AEs associated with corticosteroid use or non-steroidal immunosuppressant use, and AEs reported as laboratory abnormalities with clinical significance. Listings will be provided.

If the onset date or end date of an AE is partial, the same imputation rules described in Section 5.6 will be applied.

14.1.2 Drug-Related Adverse Events

All TEAEs assessed by investigator as study drug related (i.e., ADRs) will be summarized by SOC, PT and severity.

14.1.3 Deaths and Serious Adverse Events

Serious adverse events and SAEs assessed by investigator as study drug related (i.e., serious ADRs) will be summarized by SOC, PT and severity. Listings of deaths and all SAEs will be provided.

14.1.4 Adverse Events Causing Early Discontinuation

Adverse events that cause early discontinuation of study will be summarized by SOC, PT and severity. In addition, a list of subjects with the AEs resulting in discontinuation of study will be provided.

14.1.5 Events of Interest

The following events of interest, which include EOSI defined in the protocol, will be summarized by PT, if applicable. A list of subjects will be provided for each type of EOSI. AE profile summary including time to event onset from infusion and duration of the events will be generated for EOSI (unless otherwise specified below).

- Transaminitis
 - Alanine transaminase (ALT) elevation (Preferred term: “Alanine aminotransferase increased”).
 - AEs related to liver function, defined using the MedDRA search strategy high level term (HLT = “Liver function analyses”).
 - Potential Hy’s law cases
 - ALT or aspartate transaminase (AST) $\geq 3x$ ULN and serum TBL $> 2x$ ULN
 - Assessments of ALT/AST and TBL must be on the same day

A listing will be provided.

- Infusion-related reaction, infusion-associated reaction, Hypersensitivity, Anaphylactic or Anaphylactic reactions
 - Infusion-related reactions, defined as AEs occurring during BMN 270 infusion or within 6 hours post-infusion, will be summarized as follows:
 - Subjects who receive infusion with initial rate of approximately 4 mL/min
 - The rest of the subjects, i.e. subjects who receive infusion with initial rate of 1 mL/min
 - All treated subjects
 - Infusion-associated reactions, defined as AEs occurring within 48 hours post-infusion
 - Systemic hypersensitivity (Hypersensitivity [SMQ] – narrow scope).
 - Anaphylactic, or anaphylactoid reactions (Anaphylactic reaction [SMQ] – algorithmic) – listing only.
- Thromboembolic events:
 - Embolic and thrombotic events (SMQ) for entire study period.

- AEs suggestive of thromboembolic events: for subjects who have FVIII activity > 170 IU/dL (based on chromogenic assay) any time during study, a listing of clinical terms suggestive of thromboembolic events observed from the time point prior to when FVIII was elevated until FVIII falls below 150 IU/dL. (The preferred terms are listed in Appendix 20.2.)
- Development of anti-FVIII neutralizing antibodies (NAb) as measured by Nijmegen modified Bethesda Assay (Preferred term: “Anti factor VIII antibody positive”)
- Any new diagnosis of malignancy (except non-melanoma skin cancer)

14.1.6 Adverse Events Related to immunosuppressant therapy

Adverse events that are related to corticosteroid or non-steroidal immunosuppressant will be summarized by SOC, PT and severity. In addition, a list of subjects with the AEs related to immunosuppressant therapy will be provided.

14.2 Clinical Laboratory Tests

Clinical laboratory tests include blood chemistry, hematology, urine tests, and coagulation. Clinical laboratory test values and change from Baseline will be summarized descriptively by visit. Shift tables cross-tabulating CTCAE v4.03 grade at Baseline vs. worst CTCAE v4.03 grade at post-Baseline visits will be provided as well. A supportive listing of abnormal test values with CTCAE v4.03 grade 3 or greater will be produced.

Liver tests (LTs) by central labs will be assessed on a regular basis, as detailed in the protocol. Boxplots of maximum ALT values at 4-week intervals over time and corresponding line plots will be provided. The same analyses based on mean or median ALT values will be conducted. ALT values and change from Baseline over time will be summarized descriptively. Summaries of ALT elevations including baseline ALT, time from infusion to ALT > ULN, ALT > 3x ULN, ALT > 5x ULN, ALT > 1.5x baseline value or > ULN, , peak ALT level, and duration of ALT elevation will be provided. Local ALT assessments will be analyzed similarly as the central ALT assessments, if needed. Similar analyses will be applied to other liver tests including AST, gamma-glutamyl transferase (GGT), lactate dehydrogenase (LDH), bilirubin, and alkaline phosphatase (ALP), if needed.

In addition, incidences of potential drug-induced liver injury (DILI) that include an elevated ALT or AST in combination with either an elevated bilirubin or clinical jaundice, as defined by Hy’s law, will be summarized by count and percentage. The profile summary of the related laboratory tests results needed for determination by Hy’s law will be provided for the subjects with potential DILI.

